5.3 Description of events

Diagnosis-type medical events following MenACWY-CRM exposure in children 2-23 months of age will be described if five or more of a diagnosis or diagnosis grouping are observed. Medical events will be reviewed and summarized, at least including age at vaccination, gender, age at diagnosis, MenACWY-CRM vaccination history, setting of diagnosis, and if available, underlying condition of vaccination. Whether this is a first occurrence or recurrence of the same medical event after repeated MenACWY-CRM vaccination of the same person will be included in the description as well. See Appendix A, Table Shell 6 for details.

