9.3.3 Other Variables

- Baseline characteristics: these data will be extracted from patients' medical records.
 - Date of birth, expressed as age at vaccination
 - Gender
- Underlying condition of the MenACWY-CRM vaccine indication (i.e., persistent complement component deficiencies, asplenia or other), if available.
- Vaccination history
 - Concomitant vaccinations (specify)
 - History of other vaccinations (specify)
 - Vaccinations occurring during the observation period (specify)

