9.5 Study Size

There is no planned number of vaccinees. The study will describe all eligible medically attended events that require emergency room visit or hospitalization in the study population.

Approximately 245,000 infants and toddlers aged 2-23 months were enrolled in the KPSC health plan in the period from 2011 to 2013. Among this population, there were around 60 children aged 2-23 months old with high risk conditions. It is estimated that the number of infants with high risk conditions would likely fall between 60-100 in the study

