9.7.3 Statistical Methods

This descriptive study will analyze collected data to report frequencies of MenACWY-CRM exposure and analysis of medical events. The frequencies will be presented as absolute numbers and percentages of relevant total.

Frequency of exposure to MenACWY-CRM vaccination

This descriptive study will report the frequency of exposure among infants and toddlers 2-23 months of age vaccinated at least one dose of MenACWY-CRM during the study period. Frequency of exposure will be summarized as follows:

- Overall
- 1 dose
- 2 doses
- 3 doses
- 4 doses

Analysis of medical events

Eligible medical events in the study will be described as follows:

- Frequency of individual medical events

The frequency of medical events is defined as the total number of each individual event. The frequency will be described by absolute number of each individual medical event and percentage of each individual medical event of total number of captured medical events during the observation period.

If the number of medical events allows, captured medical events will be stratified by dose.

- Rate of medical events

The rate of medical events is defined as the number of all captured events divided by the total person-time following MenACWY-CRM doses administered during the study period. 95% confidence interval of the rate of medical events will be calculated. Person-time for each dose will begin at the vaccination and end at 6 months following vaccination, disenrollment, death, the end of data collection, or receipt of an additional dose of MenACWY-CRM, whichever comes first. If data permit, rate will be further stratified by dose.

▫ Description of medical events

Medical events following MenACWY-CRM exposure in children 2-23 months of age will be described. Medical events will be reviewed and described, at least including age at vaccination, gender, vaccination history, diagnoses, and if available, underlying condition. Recurrence of the same medical event after repeated MenACWY-CRM vaccination of the same person will be included in the description as well.

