7. STUDY REPORT

The final report will include all data generated from this study as specified in this SAP.

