Female	n (%)				
Underlying condition of index vaccine indication					
Persistent complement component deficiencies	n (%)				
Asplenia (functional, anatomic)	n (%)				
Unknown	n (%)				
Concomitant vaccinations	n (%)				
1 concomitant vaccination	n (%)				
≥ 2 concomitant vaccinations	n (%)				
vaccine 1	n (%)				
vaccine 2	n (%)				
Other*	n (%)				
Vaccinations <6 months prior to index	n (%)				
Any vaccination prior to index	n (%)				
vaccine 1	n (%)				
vaccine 2	n (%)				
Other*	n (%)				

* Includes all vaccines with less than 10 recipients

N/A = Not Applicable

† Any cell with count >0 but less than 3 is presented as "<<"

Table 3: Characteristics of MenACWY-CRM Recipients 2-23 Months of Age during the Observation Period

Characteristic	Total	Number of doses received			
		One	Two	Three	Four
MenACWY-CRM vaccination during observation period					
1 dose	n (%)				
2 doses	n (%)				
3 doses	n (%)				
Days from index vaccination to second dose	mean (sd) median Q1, Q3				
Days from second vaccination to third dose	mean (sd) median Q1, Q3				
Days from third vaccination to fourth dose	mean (sd) median Q1, Q3				
Other vaccines received during observation period					
Any vaccination during observation period	n (%)				
vaccine 1	n (%)				
vaccine 2	n (%)				
Other*	n (%)				
Other vaccines received concomitantly with subsequent MenACWY-CRM dose					
Any vaccination received concomitantly	n (%)				
vaccine 1	n (%)				
vaccine 2	n (%)				
Other*	n (%)				
Completed 6-month observation period following last dose	n (%)				
Duration of observation period (months) with censoring	mean (sd) median Q1, Q3 (min - max)				

* Includes all vaccines with less than 10 recipients during observation period

† Any cell with count >0 but less than 3 is presented as "<<"

N/A = Not Applicable

Table 4a: Summary of Hospitalization and Emergency Room Visit Event Identification and Review

Event	Automated Algorithm			Physician Review			Total Events for Analysis (g=a-b-e-f)
	Potential events identified (a)	Excluded events based on pre-existing condition (b)	Events remaining from automated identification (c=a-b)	Events confirmed (d)	Events refuted (e)	Confirmed events with diagnosis determined to be prior to index vaccination (f)	
Hospitalization only							
Emergency department only							
Emergency department and hospitalization							
Number of recipients experiencing a single hospitalization or emergency encounter							

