*The setting where the diagnosis is initially captured from our automated search, which may differ from the setting of first diagnosis found on chart review

Table 6: Description of diagnoses observed following vaccination with MenACWY-CRM

Diagnosis or diagnosis group	Age at most recent vaccination (months)	Age at first diagnosis (months)*	Gender		Setting [†]			Number of MenACWY-CRM vaccinations received prior to diagnosis			Underlying condition of vaccine indication			First occurrence or recurrence		
								One dose, %	Two doses, %	Three doses, %	Four doses, %	Persistent complement deficiencies, %	Asplenia, %	Other or Unknown, %	First occurrence, %	recurrence, %
	mean (SD)	mean (SD)	Male, %	Female, %	Inpatient, %	ED, %	Both, %	dose, %	%	%	%	%	%	%	%	%

Table includes any diagnosis or diagnosis grouping with at least five episodes confirmed by chart review

*The age of the first diagnosis in any setting for this episode, found on chart review

[†]The setting where the diagnosis is initially captured from our automated search, which may differ from the setting of first diagnosis for this episode found on chart review
SD = standard deviation

Figure 1. Number of MenACWY-CRM vaccine recipients age 2-23 months by calendar month

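### SAP 5.3 and the Table 6 footnote restrict the description of diagnoses to those with five or more episodes, while Protocol 9.7.3 sets a minimum content for describing events and no minimum count

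*SAP*

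**What the plan says.** **Protocol.** Section 9.5 states: "The study will describe all eligible medically attended events that require emergency room visit or hospitalization in the study population". Section 9.7.3 says that eligible events are presented in three forms: frequency, rate and description. For the third it sets a floor: "Medical events will be reviewed and described, at least including age at vaccination, gender, vaccination history, diagnoses" and, if available, underlying condition. It gives no minimum count for this. The two conditions in 9.7.3 that depend on the amount of data concern stratification by dose. Section 9.3.3 defines vaccination history as concomitant vaccines, earlier vaccines and vaccines given during the observation period.

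**SAP v2.0.** Section 5.3 says that diagnosis-type events "will be described if five or more of a diagnosis or diagnosis grouping are observed". The footnote to the Table 6 shell reads: "Table includes any diagnosis or diagnosis grouping with at least five episodes confirmed by chart review". The content required by 5.3 is "at least including age at vaccination, gender, age at diagnosis, MenACWY-CRM vaccination history, setting of diagnosis" and, if available, underlying condition. Sections 3.1 and 5.1 also promise description, of the events' records and of each diagnosis in its own right, and neither sets a threshold. Section 8 lists six tables and one figure, with no listing. Section 7 adds: "The final report will include all data generated from this study as specified in this SAP".

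**The concern.** The SAP puts a count condition on an element that the protocol requires without one, and does not flag this as a departure. Protocol V.2 (11 August 2016) is later than SAP v2.0 (17 November 2015) and still has no minimum count.

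At stake is descriptive content. For a diagnosis seen one to four times, the report need not say at what age, in which sex, with which underlying condition or alongside which other vaccines it occurred. The study has no comparator and no hypothesis test, and it was agreed with FDA as a post-marketing commitment, so this content is much of what a reader can use to judge an uncommon event.

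The narrower vaccination history also affects diagnoses above the cut. Co-administration is expected (Protocol 9.3.1), yet Table 6 shows only the number of MenACWY-CRM doses.

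**Working it through.** **1. Where the protocol's minimum content appears for a diagnosis seen one to four times**

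| Element (Protocol 9.7.3) | Output |
|---|---|
| Diagnosis, count, recurrences | Table 4b, no minimum |
| Overall frequency and rate | Table 5b, no minimum |
| MenACWY-CRM dose number, setting | Table 5b, subject to the n≥5 stratum rules |
| Age at vaccination, sex, underlying condition | Table 6 only, cut at five |
| Concomitant and other vaccines, linked to the event | None, for any count |

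Tables 2 and 3 describe the cohort. The Table 3 block "Other vaccines received concomitantly with subsequent MenACWY-CRM dose" counts recipients and is not tied to any event. Tables 4a and 5a count encounters and carry no descriptive fields.

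**2. Diagnosis groupings**

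A rare diagnosis can enter Table 6 inside a grouping with five or more episodes. SAP 5.2 makes grouping conditional on feasibility, and the row then shows pooled means and percentages, so the individual diagnosis is still not described.

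**3. Check of the plan's own figures**

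The only computed figures nearby are the expected confidence intervals in SAP 3.2. Exact Poisson 95% limits with x = rate × N / 100 and one person-year (PY) per child reproduce 10 of the 12 cells. The other two, both at N=50, differ by 0.1 in one limit (9.3 against 9.4; 3.2 against 3.3). The concern does not depend on that table, but the check supports using its one-PY assumption below.

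**4. Illustration of size**

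Inputs:
- Person-time of 60, 100 and 150 PY, from one PY per child (SAP 3.2). The range 60-100 is the SAP's estimate of high-risk children, not of vaccinees; 150 is its largest tabulated N.
- Diagnosis-specific rates are my assumption, because the documents give none.

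Formulas: mean m = rate × PY / 100; P(0) = exp(−m); P(1 to 4) = 1 − P(0) − P(≥5), with X Poisson. As a check for clustering within children, a negative binomial with variance 2m.

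| Rate per 100 PY | PY | m | P(0) | P(1 to 4) | P(≥5) | P(1 to 4), variance doubled | P(≥5), variance doubled |
|---|---|---|---|---|---|---|---|
| 1 | 60 | 0.6 | 0.549 | 0.451 | 0.0004 | 0.327 | 0.013 |
| 1 | 100 | 1.0 | 0.368 | 0.628 | 0.0037 | 0.469 | 0.031 |
| 1 | 150 | 1.5 | 0.223 | 0.758 | 0.0186 | 0.582 | 0.065 |
| 5 | 60 | 3.0 | 0.050 | 0.766 | 0.185 | 0.648 | 0.227 |
| 5 | 100 | 5.0 | 0.007 | 0.434 | 0.560 | 0.469 | 0.500 |
| 5 | 150 | 7.5 | 0.001 | 0.132 | 0.868 | 0.226 | 0.769 |

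An even chance of reaching five needs m = 4.67 (Poisson). That is 467/60 = 7.8, 467/100 = 4.7 or 467/150 = 3.1 per 100 PY.

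**The case against.** **Counting is itself description.** Protocol 9.7.3 lists frequency and rate among the ways events are described, and Tables 4b and 5b give both for every diagnosis without a minimum. So 9.5, a study-size statement, is partly met. This stands, and it locates the conflict in the third element of 9.7.3.

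**The SAP can be read more generously.** Section 5.1 has every diagnosis described separately, the second sentence of 5.3 carries no count, and section 7 says what the report will contain without capping it. This stands in part: the SAP is inconsistent with itself and does not clearly abandon the description. But the second sentence of 5.3 leads to Table 6, whose footnote imposes the cut, and no other planned output carries the content. An analyst following the shells would not produce it.

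**Dose number may survive.** SAP 5 does not say whether n≥5 for dose strata means recipients or events. If recipients, Table 5b could show dose number for a rare diagnosis. Age, sex, underlying condition and other vaccines would still be missing.

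**The size is hypothetical.** This is right. The rates are assumed, and children vaccinated for travel or an outbreak would add person-time. The probabilities also apply to single diagnoses, while the cut accepts groupings.

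**Privacy.** A line listing of single children with rare conditions at a named HMO carries re-identification risk. The SAP does not give this as the reason for the cut; its explicit suppression rule covers counts below 3 and is written for Tables 2 and 3. The risk is nevertheless real and shapes the fix.

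**Conclusion.** The conflict holds on the text and needs no arithmetic: Protocol 9.7.3 requires a minimum descriptive content with no minimum count, and SAP 5.3 with the Table 6 footnote supplies it only from five episodes. The narrowing of vaccination history is a second, smaller mismatch with Protocol 9.3.3. It should be fixed, at moderate priority.

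A reader might infer three stronger things that the documents do not support:
- *Rare diagnoses disappear from the report.* They do not; counts, recurrences and overall rates remain.
- *Results are biased.* No count or rate is affected.
- *Most observed diagnoses will go undescribed.* The documents give no diagnosis-specific rate, so this cannot be known.

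At an assumed 1 per 100 PY and 60 to 150 PY, the chance of one to four episodes is 45-76% and of five or more under 2% (33-58% and up to 6.5% with doubled variance). At 5 per 100 PY and 150 PY, the chance of one to four falls to 13% (23% with doubled variance). The cut therefore bears mainly on rarer diagnoses.

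**What to change.** Reconcile SAP 5.3 and the Table 6 footnote with Protocol 9.7.3 and 9.5. Suggested SAP wording:

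> The five-episode threshold governs only the summary in Table 6. Every confirmed event included for analysis whose specific diagnosis has fewer than five episodes, whether or not it also falls in a Table 6 grouping, is given in a de-identified listing.

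Listing fields: diagnosis, setting, age band, sex, MenACWY-CRM dose number, concomitant and other vaccines, underlying condition if available, and first occurrence or recurrence. The clause on groupings matters; without it, a diagnosis seen once inside a large grouping would appear only in pooled figures.

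Add event-linked concomitant and other vaccines to Table 6. Days since the most recent dose is already collected (Protocol 9.4.2, SAP 3.3.3) and would be a useful addition to both outputs, but its absence does not breach 9.7.3.

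**Cost.** SAP wording, one listing and added Table 6 columns, from data already collected. The main downside is re-identification: a small cohort, rare conditions, and waivers of consent and HIPAA authorization to be requested (Protocol 10.3). The existing display rules cover Tables 2 and 3 and strata, so the listing needs its own disclosure rule, for example full detail to the sponsor and regulator and a coarsened public version. That means a privacy review and possibly two versions of the listing.

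**Alternative.** Amend the protocol to state the threshold and its reason. This removes the conflict but gives up the description of rarer diagnoses.

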5.4 Sensitivity analysis

No sensitivity analyses are planned.

6. STATISTICAL CONSIDERATIONS AND LIMITATIONS

6.1 Statistical considerations

Due to the expected small sample size, no formal hypothesis testing or statistical analysis is planned.

6.2 Internal Validity

Misclassification of diagnosis

As this study focuses on medical events requiring hospitalization and emergency care among children 2-23 months of age enrolled as KPSC health plan members, it is unlikely that serious and acute outcomes would be missed or misclassified. Also, due to the ICD-9 to ICD-10 transition, both ICD-9 and ICD-10 codes may need to be searched to exclude pre-existing conditions. Some pre-existing conditions may be missed from the automated search due to imperfect mapping between ICD-9 and ICD-10.

Misclassification of exposure

Depending on the available data in the medical record database on the recording of a vaccination, it may be that not all vaccinations are given through the HMO, resulting in not all vaccination data being present in the medical record. As vaccinations are available at no cost to members of the HMO, we expect that very few vaccinations will be received outside of the HMO. However, loss of these data should not affect results because analyses are confined to those individuals with a recorded vaccine administration.

Missing Data

No imputation will be performed. We expect there to be a very low rate of missing data regarding population characteristics, such as age and gender, and diagnoses. The study uses EMRs as the source of information for diagnoses, so events that do not result in a medical visit may be missed. Subjects missing the stratification factors will be excluded from subgroup analysis where the stratification factor is unknown. We expect that most vaccines will be captured by the EMR, with very little missing information. It is possible that some study subjects will have received meningococcal vaccine prior to joining the health plan, and these prior doses may not be captured. This number is expected to be small and not to have a material impact on the results.

Handling of Loss to Follow-up

We expect there to be minimal loss to follow-up due to the high retention of KPSC health plan members in this age group. Any loss will be addressed in the data analysis by the truncation of person-time in the event rate calculation.

7. STUDY REPORT

The final report will include all data generated from this study as specified in this SAP.

8. LIST OF REPORT TABLES, LISTINGS AND FIGURES

	Population* (all or per event)	Description	Strata**
Table 1	All	Study population selection	
Table 2	All	Baseline Characteristics of MenACWY-CRM recipients 2-23 months of age	Number of vaccinations received
Table 3	All	Follow-up characteristics of MenACWY-CRM recipients 2-23 months of age	Number of vaccinations received
Table 4	Per event	Summary of event identification and review	
Table 5	Per event	Frequency and rate of events among infant MenACWY-CRM recipients	Number of vaccinations received, care setting (5b only), recurrence (5b only)
Table 6	Per event	Description of diagnoses among infant MenACWY-CRM recipients	
Figure 1	All	Vaccinations by Month	Number of vaccinations received

*All = all MenACWY-CRM recipients,

Per event will include all recipients with no history of that event prior to the first MenACWY-CRM dose

** Data are only presented in stratum if sufficient numbers are available in each stratum ($n \geq 5$).

9. QUALITY CONTROL

9.1 Data Management

Data for this study will include vaccination, demographics, membership, utilization, death, and data from the identification and validation of serious medically-attended events that may occur in the six months following vaccination. The contents of the various datasets are specified separately in a data dictionary, which will be provided with the relevant SAS programming.

9.2 Data Quality Checks

Range checks and general frequency tables will be produced such that missing values, outliers, and inappropriate or abnormal values will be identified. Comparisons between date of birth, date of death, event dates and vaccination dates will be made. All data will be checked for duplicate records.

A record of data quality problems and resolutions will be kept in the form of an Excel spreadsheet or other method appropriate to the circumstances (e.g. commented code, detailed correspondence). All inconsistencies and/or data quality issues will be documented. Revisions will be noted in order to capture the change made, the change date, identification of the individual making the change, as well as noting any further actions to be taken to identify and/or resolve additional data quality problems of this type.

All programming will be reviewed by a second programmer. Additionally, prior to reviewing the original programming, the second programmer will independently extract vaccination data. The results of the original and validation programming will be compared and any discrepancies will be investigated. A report will be created, listing discrepancies, their causes, and any action taken to resolve them. It is expected that there may be a small number of discrepancies due to a difference in the date on which the original and validation programs are run, as they are pulling from live databases which are updated regularly. If this cause is suspected, both programs may be run again on the same date as a means to eliminate this potential cause of discrepancies.

9.3 Confidentiality of Data

Any research data containing subject protected health information (PHI) is confidential. KPSC staff will not discuss the protocol or research data with anyone other than KPSC project personnel, or representatives of GSK. All sharing of confidential information shall be in accordance with the confidentiality agreement detailed in the study contract.

Appendix A: Table shells

Table shells are provided in a separate Excel file.

Appendix B: Underlying condition of vaccine indication

Vaccine recipients will be determined to have the following underlying conditions for vaccination if the associated diagnosis codes are present in the medical record six months prior to index vaccination, including the date of index vaccination.

1. Asplenia

Functional - Hemoglobinopathies (primarily sickle cell [SS or SC] disease)

ICD-9 Codes:

Diagnosis	ICD-9 Diagnostic Code
Sickle cell disease unspecified	282.60
HB-SS disease with crisis	282.62
Sickle cell thalassemia without crisis	282.41
Sickle cell/HB-C disease without crisis	282.63
Sickle cell/HB-C disease with crisis	282.64
Other sickle cell disease without crisis	282.68
Other sickle cell disease with crisis	282.69
Sickle cell thalassemia with crisis	282.42

ICD-10 Codes:

Diagnosis	ICD-10 Diagnostic Code
Sickle cell disease without crisis	D57.1
HB-SS disease with crisis, unspecified	D57.00
Sickle cell thalassemia without crisis	D57.40
Sickle cell/HB-C disease without crisis	D57.20
Sickle cell/HB-C disease with crisis, unspecified	D57.219
Other sickle cell disorders without crisis	D57.80

Other sickle cell disease with crisis, unspecified	D57.819
Sickle cell thalassemia with crisis, unspecified	D57.419
Hyposplenism	D73.0

Anatomic Asplenia

ICD-9 Codes:

Diagnosis	ICD-9 Diagnostic Code
Anomalies of spleen congenital	759.0

ICD-10 Codes:

Diagnosis	ICD-10 Diagnostic Code
Asplenia (congenital)	Q89.01
Congenital malformations of spleen	Q89.09
Acquired asplenia	Z90.81

2. Persistent Complement Component Deficiencies

ICD-9 Codes:

Diagnosis	ICD-9 Diagnostic Code
Other specified disorders involving the immune mechanism	279.8

ICD-10 Codes:

Diagnosis	ICD-10 Diagnostic Code
-----------	------------------------

Defects in the complement system	D84.1
----------------------------------	-------

Table 1: Study population selection

Population	Total (n)
Total number of persons within the KPSC cohort	
Total number of children 2-23 months old in the KPSC cohort	
Total MenACWY-CRM vaccine recipients among age 2-23 months	

Date tables created:

Period captured in the tables:

Report integrates the tables:

Table 2: Baseline Characteristics of MenACWY-CRM Recipients 2 to 23 Months of Age

Characteristic	Total	Number of doses received			
		One	Two	Three	Four
Age at first vaccination (months)	mean (sd) median Q1, Q3 (min - max)				
Age 2-6 months at first vaccination	n (%)				
Age 7-23 months at first vaccination	n (%)				
Gender					
Male	n (%)				
Female	n (%)				
Underlying condition of index vaccine indication					
Persistent complement component deficiencies	n (%)				
Asplenia (functional, anatomic)	n (%)				
Unknown	n (%)				
Concomitant vaccinations	n (%)				
1 concomitant vaccination	n (%)				
≥ 2 concomitant vaccinations	n (%)				
vaccine 1	n (%)				
vaccine 2	n (%)				
Other*	n (%)				
Vaccinations <6 months prior to index	n (%)				
Any vaccination prior to index	n (%)				
vaccine 1	n (%)				
vaccine 2	n (%)				
Other*	n (%)				

* Includes all vaccines with less than 10 recipients

N/A = Not Applicable

† Any cell with count >0 but less than 3 is presented as "<<"

Table 3: Characteristics of MenACWY-CRM Recipients 2-23 Months of Age during the Observation Period

Characteristic	Total	Number of doses received			
		One	Two	Three	Four
MenACWY-CRM vaccination during observation period					
1 dose	n (%)				
2 doses	n (%)				
3 doses	n (%)				
Days from index vaccination to second dose	mean (sd) median Q1, Q3				
Days from second vaccination to third dose	mean (sd) median Q1, Q3				
Days from third vaccination to fourth dose	mean (sd) median Q1, Q3				
Other vaccines received during observation period					
Any vaccination during observation period	n (%)				
vaccine 1	n (%)				
vaccine 2	n (%)				
Other*	n (%)				
Other vaccines received concomitantly with subsequent MenACWY-CRM dose					
Any vaccination received concomitantly	n (%)				
vaccine 1	n (%)				
vaccine 2	n (%)				
Other*	n (%)				
Completed 6-month observation period following last dose	n (%)				
Duration of observation period (months) with censoring	mean (sd) median Q1, Q3 (min - max)				

* Includes all vaccines with less than 10 recipients during observation period

† Any cell with count >0 but less than 3 is presented as "<<"

N/A = Not Applicable

Table 4a: Summary of Hospitalization and Emergency Room Visit Event Identification and Review

Event	Automated Algorithm			Physician Review			Total Events for Analysis (g=a-b-e-f)
	Potential events identified (a)	Excluded events based on pre-existing condition (b)	Events remaining from automated identification (c=a-b)	Events confirmed (d)	Events refuted (e)	Confirmed events with diagnosis determined to be prior to index vaccination (f)	
Hospitalization only							
Emergency department only							
Emergency department and hospitalization							
Number of recipients experiencing a single hospitalization or emergency encounter							
Number of recipients experiencing multiple different hospitalization or emergency encounters							
N/A = Not Applicable							

Table 4b: Summary of Diagnosis Identification and Review

Event	Automated Algorithm			Physician Review			Diagnosis is continuation of an ongoing episode (g)	Diagnosis is a recurrence (h)	Total Diagnoses for Analysis (i=a-b-e-f-g)
	Potential diagnoses identified (a)	Excluded diagnoses based on pre-existing condition (b)	Diagnoses remaining from automated algorithm identification (c=a-b)	Diagnoses confirmed (d)	Diagnoses refuted (e)	Confirmed events with diagnosis determined to be prior to index vaccination (f)			
Specific diagnoses									
diagnosis 1									
diagnosis 2									
Diagnosis groupings									
grouping 1									
grouping 2									
Number of recipients experiencing a single diagnosis									
Number of recipients experiencing multiple different diagnoses									

N/A = Not Applicable

Table 5a: Frequency and rate of hospitalization and emergency events observed following vaccination with MenACWY-CRM

Event	Overall		Number of vaccines received prior to event							
			One		Two		Three		Four	
	Frequency n (%)	Rate (95% CI)*	Frequency n (%)	Rate (95% CI)*	Frequency n (%)	Rate (95% CI)*	Frequency n (%)	Rate (95% CI)*	Frequency n (%)	Rate (95% CI)*
Hospitalization only										
Emergency department only										
Emergency department and hospitalization										

*Events per 1000 person years

Table 5b: Frequency and rate of diagnoses observed following vaccination with MenACWY-CRM

Event	Overall		Number of vaccines received prior to event								Setting of initial presentation with the diagnosis*						First occurrence or recurrence			
			One		Two		Three		Four		Inpatient		Emergency		Both settings		First occurrence		Recurrence	
	Frequency n (%)	Rate (95% CI)*	Frequency n (%)	Rate (95% CI)*	Frequency n (%)	Rate (95% CI)*	Frequency n (%)	Rate (95% CI)*	Frequency n (%)	Rate (95% CI)*	Frequency n (%)	Rate (95% CI)*	Frequency n (%)	Rate (95% CI)*	Frequency n (%)	Rate (95% CI)*	Frequency n (%)	Rate (95% CI)*	Frequency n (%)	Rate (95% CI)*
Specific diagnoses																				
diagnosis 1																				
diagnosis 2																				
Diagnosis groupings																				
grouping 1																				
grouping 2																				
etc.																				

*Events per 1000 person years

*The setting where the diagnosis is initially captured from our automated search, which may differ from the setting of first diagnosis found on chart review

Table 6: Description of diagnoses observed following vaccination with MenACWY-CRM

Diagnosis or diagnosis group	Age at most recent vaccination (months)	Age at first diagnosis (months)*	Gender		Setting [†]			Number of MenACWY-CRM vaccinations received prior to diagnosis			Underlying condition of vaccine indication			First occurrence or recurrence		
								One dose, %	Two doses, %	Three doses, %	Four doses, %	Persistent complement deficiencies, %	Asplenia, %	Other or Unknown, %	First occurrence, %	recurrence, %
	mean (SD)	mean (SD)	Male, %	Female, %	Inpatient, %	ED, %	Both, %	dose, %	%	%	%	%	%	%	%	%

Table includes any diagnosis or diagnosis grouping with at least five episodes confirmed by chart review

*The age of the first diagnosis in any setting for this episode, found on chart review

[†]The setting where the diagnosis is initially captured from our automated search, which may differ from the setting of first diagnosis for this episode found on chart review
SD = standard deviation

Figure 1. Number of MenACWY-CRM vaccine recipients age 2-23 months by calendar month
